7.13 Pharmacokinetics (PK) and Pharmacodynamics (PD)

Table 15: Specimens Collected to Assess Safety, PK and Ex Vivo Antiviral Activity

Study Visit	Specimens collected for PK, PD and subclinical safety – Females only		
	Blood	CVF	CVT
Visit 2	
 • Plasma for PK (pre-dose & 6hr post-dose) • PBMC for TFV-DP (pre-dose) 	
 • CVF for PK (pre-dose & 6hr post-dose) • CVF for PD (pre-dose & 6hr post-dose) 	
Visit 3	
 • Plasma for PK • PBMC for TFV-DP 	
 • CVF for PK • CVF for PD 	
 • 2 BXV for PK • 1 BXV for IHC
Visit 4	
 • Plasma for PK • PBMC for TFV-DP 	
 • CVF for PK • CVF for PD 	
Visits 5 (6hr post-dose)	
 • Plasma for PK 	
 • CVF for PK • CVF for PD 	
Visit 6	
 • Plasma for PK • PBMC for TFV-DP 	
 • CVF for PK • CVF for PD 	
 • 2 BXV for PK • 1 BXV for IHC
Visit 7	
 • Plasma for PK • PBMC for TFV-DP 	
 • CVF for PK • CVF for PD 	
Visit 8 (6hr post-dose)	
 • Plasma for PK 	
 • CVF for PK • CVF for PD 	
Visit 9	
 • Plasma for PK • PBMC for TFV-DP 	
 • CVF for PK • CVF for PD 	
 • 2 BXV for PK • 1 BXV for IHC
Visit 10	
 • Plasma for PK • PBMC for TFV-DP 	
 • CVF for PK • CVF for PD 	

7.14 Specimen Management

Study sites will adhere to the standards of good clinical laboratory practice, in accordance with the MATRIX-004 SSP Manual and site-specific SOPs for proper collection, processing, labeling,

transport, and storage of specimens. Specimen collection, testing, and storage at the site laboratories will be documented when applicable using the Laboratory Data Management System (LDMS). In cases where laboratory results are not available due to administrative or laboratory error, or out of range and the site IoR/designee determines that it is reasonable to repeat, the site is permitted to re-draw specimens. No genetic testing (limited or genome-wide) is planned on leftover samples.

7.15 Laboratory Oversight

All laboratories participating in this study will adhere to MATRIX's Laboratory Policy (www.matrix4prevention.org).

7.16 Biohazard Containment

As the acquisition of HIV and other blood-borne pathogens can occur through contact with contaminated needles, blood, and blood products, appropriate blood and secretion precautions will be employed by all personnel in the drawing of blood and shipping and handling of all specimens for this study as recommended by the CDC, National Institutes of Health (NIH), and all other applicable national regulatory authorities. All biological specimens will be transported using packaging mandated by Code of Federal Regulations (CFR) 42 Part 72. All dangerous goods materials, including diagnostic specimens and infectious substances, must be transported according to instructions detailed in the International Air Transport Association (IATA) Dangerous Goods Regulations. Biohazardous waste will be contained according to institutional, transportation/carrier, and all other applicable regulations.

8 ASSESSMENT OF SAFETY

8.1 Safety Monitoring

Site IoRs/designees are responsible for continuous close safety monitoring of all study participants, and for alerting the Management Team and/or PSRT if unexpected concerns arise. A sub-group of the Protocol Team, including the Protocol Co-Chairs, Protocol Safety Physician, Clinical Research Manager(s) (CRM), Data Manager(s) (DM) and CONRAD representatives will serve as the PSRT. The DM prepares routine AE and clinical data reports for review by the PSRT, which meets via conference call approximately once per month or more frequently as needed throughout the period of study implementation to review safety data, discuss product use management, and address any potential safety concerns.

8.2 Clinical Data and Safety Review

A multi-tiered safety review process will be followed for the duration of this study. The site IoRs/designees are responsible for the initial evaluation and reporting of safety information at the participant level and for alerting the PSRT if unexpected concerns arise. Participant safety is also monitored at the project level through routine reviews conducted by the PSRT and study sponsors. Additional reviews may be conducted at each of these levels as dictated by the occurrence of certain events.

The DM(s) will review incoming safety data on an ongoing basis. Events identified as questionable, inconsistent, or unexplained will be queried for verification. To ensure prompt review of AEs of concern (e.g., serious adverse events [SAE] and Related Grade 3+ AEs), such AEs submitted in the clinical database can be forwarded to the PSRT for review within 72 hours of entry.

The PSRT will meet approximately every month, or as needed, via conference call to review clinical data reports generated by the DM(s). The content, format and frequency of the clinical data reports will be agreed upon by the PSRT and the DM(s) in advance of study implementation. In addition to the routine safety data reviews, the PSRT will convene on an ad hoc basis to make decisions regarding the handling of any significant safety concerns. If necessary, experts external to MATRIX representing expertise in the fields of microbicides, biostatistics, HIV acquisition and medical ethics may be invited to join the PSRT safety review. A recommendation to pause or stop the trial may be made by the PSRT at this time or at any such time that the team agrees that an unacceptable type and/or frequency of AEs has been observed.

The Independent Safety Physician (ISP) will review participant safety data as part of their regular reviews (see Section 10.7.1), since no Data and Safety Monitoring Board (DSMB) oversight is planned for MATRIX-004. These reviews will take place approximately every 3 months, or as needed. The ISP will be an independent investigator(s) with no interest (financial or otherwise) in the outcomes of this study. At the time of these reviews, or at any other time, the ISP or PSRT may convene a panel (composed of the ISP, PSRT and protocol statistician[s]) to review study findings. This panel may recommend that the study proceed as designed, proceed with design modifications, or be discontinued. If at any time a decision is made to discontinue enrollment and/or study product use in all participants, CONRAD will notify USAID, the US Food and Drug Administration (FDA), Gilead, and any investigators conducting studies under the same IND, and the site IoRs/designees will notify the responsible IRBs/IECs and applicable national drug regulatory authorities (DRA) expeditiously per local guidelines.

8.3 Adverse Events Definitions and Reporting Requirements

8.3.1 Adverse Events

An AE is defined as any untoward medical occurrence in a clinical research participant administered an investigational product and which does not necessarily have a causal relationship with the investigational product. As such, an AE can be an unfavorable or unintended sign (including an abnormal laboratory finding, for example), symptom or disease temporally associated with the use of an investigational product, whether or not considered related to the product. This definition is applied to all study participants and is applied beginning after product use at the enrollment visit. The term “investigational products” for this study refers to the TAF/EVG vaginal insert, 20/16 mg. AEs should be assessed for relatedness to investigational product and to study procedures.

Study participants will be provided instructions for contacting the study site to report any untoward medical occurrences they may experience. In cases of potentially life-threatening events, participants will be instructed to seek immediate emergency care. Where feasible and medically appropriate, participants will be encouraged to seek evaluation where a study clinician is based. With appropriate permission of the participant(s), whenever possible, records from all

non-study medical providers related to untoward medical occurrences may be sought if necessary to obtain clinically relevant information for the study and required data elements will be recorded on study CRFs. All participants reporting an untoward medical occurrence will be followed clinically until the occurrence resolves (returns to baseline) or stabilizes, per clinical discretion.

Study site staff will document in source documents and in the study database all AEs reported by or observed in enrolled study participants regardless of severity and presumed relationship to study product. AE severity will be graded per the DAIDS Table for Grading Adult and Pediatric Adverse Events, Corrected Version 2.1, July 2017 and/or Addenda 1 (Female Genital Grading Tables for Use in Microbicide Studies [Dated November 2007]).

For any SAEs that are continuing at SEV, the IoR/designee must establish a clinically appropriate follow-up plan for the AE. At a minimum, the SAE must be re-assessed by study staff within 30 days after the SEV; additional evaluations also may take place at the discretion of the IoR/designee. The same approach must be taken for any AEs that are found to have increased in severity at the SEV, for any new AEs found at the SEV, and for participants who permanently discontinue study product use due to a product-related AE. For those AEs requiring re-assessment, if the AE has not resolved or stabilized at the time of re-assessment, study staff will continue to re-assess the participant(s) while the study is ongoing, per IoR/designee discretion. For AEs that are re-assessed after study exit, information on the status of the AE at the time of re-assessment will be recorded in source documents only — no updates should be made to AE CRFs based on the re-assessments; see Section 9.5 for exceptions related to updating CRFs post-SEV to document pregnancy outcomes, should they occur during the study.

After the study has ended, the PSRT may advise study staff on a case-by-case basis as to whether any additional follow-up may be indicated for AEs that have not resolved or stabilized.

8.3.2 Serious Adverse Events

As per the International Council for Harmonization of Technical Requirements for Pharmaceuticals for Human Use Good Clinical Practice Guidance (ICH E6; <https://www.ich.org/page/efficacy-guidelines>), SAEs are defined as AEs occurring at any dose that:

- Results in death
- Is life-threatening
- Results in persistent or significant disability/incapacity
- Is a congenital anomaly/birth defect
- Requires inpatient hospitalization or prolongation of existing hospitalization

NOTE: Per ICH SAE definition, hospitalization itself is not an AE, but is an outcome of the event. Thus, hospitalization in the absence of an AE is not regarded as an AE. The following are examples of hospitalization that are not considered to be AEs:

- Protocol-specified admission (e.g., for procedure required by study protocol)
- Admission for treatment of target disease of the study, or for pre-existing condition (unless it is a worsening or increase in frequency of hospital admissions as judged by the clinical investigator)

- Diagnostic admission (e.g., for a work-up of an existing condition such as persistent pretreatment lab abnormality)
- Administrative admission (e.g., for annual physical)
- Social admission (e.g., placement for lack of place to sleep)
- Elective admission (e.g., for elective surgery)

Important medical events that may not result in death, be life-threatening, or require hospitalization may be considered a serious adverse drug experience when, based upon appropriate medical judgment, they may jeopardize the participant and may require medical or surgical intervention to prevent one of the outcomes listed above.

Any SAE including those listed in the protocol, investigator brochure, or package insert must be reported to CONRAD within 24 hours of discovery. If there is any question whether the event meets the criteria for “serious” it should be reported anyway. In addition, a completed SAE form must be emailed to CONRAD ([contact]) as soon as possible.

8.3.3 Adverse Event Relationship to Study Product

Relatedness is an assessment made by a study clinician of whether or not the event is related to the study agent. The PSRT will review and confirm relatedness. The relationship categories that will be used for this study are:

- Related: There is a reasonable possibility that the AE may be related to the study agents
- Not Related: There is not a reasonable possibility that the AE is related to the study agents

8.4 Pregnancy and Infant Outcomes

Pregnant women are excluded from this study.

A participant who is pregnant after enrollment will continue to be followed until the pregnancy outcome is ascertained, and information collected on the infant(s) up to approximately one year after delivery for those pregnancies that result in live birth. A participant who becomes pregnant during the study will have study product discontinued (if initiated) and will be terminated from the study. Please see Section 9.5 for additional details.

8.5 Regulatory Requirements

AEs reported on CRFs will be included in reports to the FDA and other applicable national DRA. Site IoRs/designees will submit AE information in accordance with local and national regulatory agencies’ or other local and national authorities’ requirements. Site IoRs/designees also will submit AE information and any other relevant safety information to their IRBs/IECs and national DRA in accordance with IRB/IEC/DRA requirements.

8.6 Social Harms Reporting

Although study sites will make every effort to protect participant privacy and confidentiality, it is possible that participants’ involvement in the study could become known to others and that social harms may result. For example, participants could be treated unfairly, or could have problems

being accepted by their families, partners and/or communities. Social harms that are judged by the IoR/designee to be serious or unexpected will be reported to the PSRT and responsible site IRBs/IECs according to their individual requirements. In the event that a participant reports social harm, every effort will be made by study staff to provide appropriate care and counseling to the participant, and/or referral to appropriate resources for the safety of the participant as needed. While maintaining participant confidentiality, study sites may engage their community advisory boards (CABs) in exploring the social context surrounding instances of social harm.

9 CLINICAL MANAGEMENT

Guidelines for clinical management and temporary product hold/permanent discontinuation of study product are outlined in this section. In general, the IoR/designee has the discretion to hold study product temporarily at any time if s/he feels that continued product use would be harmful to the participant or interfere with treatment deemed clinically necessary. Unless otherwise specified below, the IoR/designee should immediately consult the PSRT for further guidance on resuming study product, continuing the hold temporarily, or progressing to permanent discontinuation of study product. The IoR/designee will document all temporary product holds and permanent discontinuations on applicable CRFs.

9.1 Grading System

AE severity grading is described in Section 8.3.

9.2 Dose Modification Instructions

No dose modifications will be undertaken in this study.

9.3 General Criteria for Temporary Hold and Permanent Discontinuation of Study Product

A participant will be permanently discontinued from product use by the IoR/designee for any of the following reasons:

- Failure to follow protocol requirements that is judged severe enough by the investigator to significantly affect study outcomes
- HIV or STI acquisition
- Pregnancy or expresses a desire to become pregnant
- SAEs or other serious medical reasons, as judged by the IoR/designee to clinically warrant permanent discontinuation

A participant will be temporarily held from product use by the IoR/designee for any of the following reasons:

- Grade 2 related or higher AE/SAE where short-term resolution is possible, if assessed by the IoR/designee to clinically warrant a product hold

The IoR/designee must consult the PSRT on all temporary product holds for further guidance on resuming product use, continuing the temporary hold, or progressing to permanent

discontinuation. If product use is temporarily held/permanently discontinued at IoR/designee discretion, but the underlying reason for the temporary hold later resolves, the IoR/designee should consult the PSRT to resume product use at that time. All AEs are defined by the DAIDS Table for Grading the Severity of Adult and Pediatric Adverse Events, as outlined in Section 8.3.

9.4 HIV Infection

Potential participants who test positive for HIV prior to eligibility confirmation will be excluded from the study but will be referred to HIV care and management without delay. Participants who test positive for HIV after eligibility confirmation must have study product permanently discontinued by the IoR/designee. A participant who is confirmed to be HIV positive during the study will have all follow-up visits discontinued and the participant will be considered terminated from the study as per Section 7.6.1. Participants identified as infected with HIV are managed or referred for management according to the local standard of care. Guidance regarding management and referral for participants confirmed to be HIV-positive can be found in Section 13.10. Sites will not be responsible for paying for HIV-related care.

9.5 Pregnancy

Pregnancy testing will be performed at designated study visits and participants will be encouraged to report all signs or symptoms of pregnancy to study staff. The IoR/designee will counsel any participant who becomes pregnant regarding possible risks to the fetus. The IoR/designee also will refer the participant to all applicable services; however, sites will not be responsible for paying for pregnancy-related care.

Potential participants who test positive for pregnancy prior to eligibility confirmation will be excluded from the study but will be referred to all applicable services. Participants who test positive for pregnancy after eligibility confirmation will have study product discontinued and will be terminated from the study as per Section 7.6.2. A participant who is pregnant at study termination will continue to be followed until the pregnancy outcome is ascertained (or, in consultation with the PSRT, it is determined that the pregnancy outcome cannot be ascertained). Pregnancy outcomes will be reported on relevant CRFs; outcomes meeting criteria for SAE reporting also will be reported on the Adverse Event CRF. The study site will make every reasonable effort to contact participants and collect information on the infant(s) up to approximately one year after delivery for those pregnancies that result in live birth.

9.6 Criteria for Early Termination of Study Participation

Participants may voluntarily withdraw from the study for any reason at any time. IoRs/designees also may withdraw participants from the study to protect their safety and/or if they are unwilling or unable to comply with required study procedures, after consultation with the PSRT. Participants also may be withdrawn if CONRAD, USAID, MATRIX, government or regulatory authorities, including the FDA and Office for Human Research Protections (OHRP), or site IRBs/IECs/DRAs terminate the study prior to its planned end date. Every reasonable effort is made to complete a final evaluation of both participants if one or both withdraw or are withdrawn from the study prior to completing follow-up (see details regarding the Early Termination Visits for male and female participants in Section 7.5.1 and Section 7.5.3, respectively). Study staff members will record the reason(s) for all withdrawals in participants' study records.

10 STATISTICAL CONSIDERATIONS

10.1 Overview and Summary of Design

MATRIX-004 is a Phase 1 randomized study evaluating the impact of vaginal sexual intercourse (coitus) on the TAF/EVG insert when administered vaginally before and after coitus. MATRIX-004 will examine the PK, PD, general and mucosal safety, and acceptability of inserts containing the combination of TAF and EVG applied vaginally, before and after coitus.

10.2 Study Endpoints

Primary Endpoints

PK

- Concentrations of TFV, TAF and EVG in plasma after dosing
- Concentrations of TFV, TAF and EVG in CVF after dosing
- Concentrations of TFV, TFV-DP, TAF and EVG in CVT after dosing
- Concentrations of TFV-DP in PBMC after dosing

Secondary Endpoints

Acceptability

- Responses to key questions on overall experience (e.g., satisfaction, comfort) with using the TAF/EVG insert before and after coitus

Safety

- Any Grade 2 or higher TEAE

Exploratory Endpoints

PD

- Anti-HIV activity in CVF obtained at baseline and after dosing

Impact of coitus on TAF/EVG vaginal insert mucosal safety

- Changes in mucosal microenvironment and histology (epithelial integrity and immune cell infiltrate)

10.3 Primary Study Hypothesis

It is hypothesized that there will be no clinically significant change in PK endpoints from baseline when the TAF/EVG Insert, 20/16 mg, is administered vaginally by healthy, non-pregnant, HIV-uninfected adult women at low risk for HIV acquisition before and after vaginal sexual intercourse (coitus).

10.4 Sample Size and Power Calculations

Based on previous findings on the impact of sex on TFV vaginal gel from MTN-011¹⁸ and focusing on observed differences in TFV-DP concentrations in vaginal tissue, we would need about 20 female participants (10 per group) to detect a similar effect size (~65%) with 80% power at a 0.05 significance level. We are planning to enroll 32 couples to complete at least 28 to provide sufficient power to analyze effect differences per site. Altogether, this sample size will provide 80% power to detect a minimum of 55% difference in TFV-DP concentration (effect size) at 5% level of significance.

Qualitative data collection

Up to 40 study participants (6-10 female and 6-10 male per site) will be purposively selected and invited to complete an IDI after V8 but before exiting the study.

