4.7 Sites

The study will be conducted at two sites: VHS in the United States and CAPRISA eThekweni in South Africa.

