10.6 Participant Accrual, Follow-up and Retention

A sufficient number of couples may be consented and undergo assessment procedures in order to have approximately 32 (16 in each site) evaluable couples, i.e., couples that complete all study visits. All participants that undergo baseline sampling will be included in the analysis. Participants who initiate product use but discontinue the study prior to completion may not re-enroll. If either partner (female or male) discontinues the study early, the couple will be discontinued from the study early. Participants who discontinue the study early may be replaced to reach the target of having approximately 32 couples with complete study data. Replacement participants will be assigned to the same group (1hr or 4hr) as the withdrawn participants to avoid bias.

NOTE: Per Section 10.4, a maximum of 4 couples across the 2 study sites (up to 2 per randomization group) may discontinue the study early without requiring that the participants be replaced while still achieving sufficient power to analyze effect differences per site.

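### Sections 10.4 and 10.6 claim sufficient power per site, but each site has 14 to 16 women where the protocol's own calculation needs 20; per-site power is about 60-70%

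*Protocol*

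**What the plan says.** Protocol Section 10.4 bases the sample size on an earlier study of sex and tenofovir gel, "focusing on observed differences in TFV-DP concentrations in vaginal tissue". It makes three statements in turn:

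- The requirement: "we would need about 20 female participants (10 per group) to detect a similar effect size (~65%) with 80% power", at a significance level of 0.05.
- The per-site claim: "We are planning to enroll 32 couples to complete at least 28 to provide sufficient power to analyze effect differences per site".
- The overall claim: "this sample size will provide 80% power to detect a minimum of 55% difference in TFV-DP concentration (effect size) at 5% level of significance". Its opening word marks this as a statement about the whole sample.

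Section 4.7 names two sites. Section 10.6 plans 16 evaluable couples at each, and Section 6.1 randomizes 1:1 at each site. The note in Section 10.6 lets up to four couples, at most two per randomization group, go unreplaced "while still achieving sufficient power to analyze effect differences per site". It sets no limit per site.

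**The concern.** The requirement and the per-site claim stand in adjacent sentences and cannot both hold. If 20 women give 80% power for the 65% effect, 14 or 16 women at a site give less. The only power standard in the section is 80%, stated just before and just after the claim, so that is how "while still achieving sufficient power to analyze effect differences per site" will be read.

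Two things are at stake. The protocol credits the design with a property it lacks. That matters somewhat more here because the primary hypothesis (Section 10.3) is of no clinically significant change, so a non-significant result at one site could be taken as support. Second, the note on unreplaced drop-outs in Section 10.6 gives per-site power as its reason, and that reason is wrong.

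**Working it through.** **Inputs from the protocol.** 20 women, 10 per group, for a 65% effect with 80% power at 0.05 (10.4); 32 couples planned, at least 28 completing (10.4); two sites (4.7); 16 couples per site and up to four unreplaced losses (10.6); 1:1 randomization at each site (6.1).

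**Assumptions.** The protocol gives no standard deviation, test or sidedness for this calculation. I take a two-sided test and, because Section 10.7.4 rules out transformation, the untransformed scale. The standard deviation is solved from the protocol's own requirement.

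**Step 1: reproduce the 55% figure.** For fixed power, the detectable effect scales with 1/√n. Going from 10 to 14 per group (28 completers, sites pooled): 65% × √(10/14) = 54.9%. Power at 55% with 14 per group is 80.1% (normal approximation) or 81.5% (two-sample t). The 65% and 55% figures agree with each other, and 55% belongs to the pooled sample.

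**Step 2: women per site.** 32/2 = 16, or 8 per group. 28/2 = 14, or 7 per group, with losses split evenly. If all four losses fall at one site, two from each group, 16 − 4 = 12, or 6 per group. All are below 10 per group.

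**Step 3: per-site power for the 65% effect.** For each test, find the standardized effect d that gives 80% power at the protocol's 20 women, then apply it at the site's size. The noncentrality is d√(n/2) for two groups of n, and d√n for n pairs.

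| Test calibrated to 20 women | d | 12 at site | 14 at site | 16 at site |
|---|---|---|---|---|
| Two-sample t, 10 per group | 1.325 | 54.5% | 62.5% | 69.3% |
| Paired t within a timing group, 10 pairs | 0.996 | 50.4% | 59.7% | 67.7% |
| Paired t over all 20 women | 0.660 | 55.0% | 62.8% | 69.5% |

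The normal approximation for two groups gives 58%, 65% and 71%. One-sided testing gives about 64-67% with 14 women and 70-72% with 16. None reaches 80%.

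**Step 4: effect detectable per site with 80% power.** As an approximation, 65% × √(10/7) = 77.7% with 14 women and 65% × √(10/8) = 72.7% with 16. The three t-based versions give 80-83% with 14 and 74-75% with 16.

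**Step 5: pooled power.** With 28 completers, the two-sample t gives 92% for the 65% effect and 81.5% for 55%.

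**The case against.** The strongest defence is that the main comparisons in Section 10.7.2 are within-woman. If 10 per group meant that a paired test needs only 10 women, and both timing groups were pooled within a site, per-site power would be 93% with 14 women and 96% with 16. Because Section 10.4 names no test, this reading cannot be excluded outright. But the section counts 20 women, and Section 10.7.2 plans the paired and repeated-measures analyses separately for the 1-hour and 4-hour groups. Within one group a site has 7 or 8 women against 10.

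Three further points for the sponsor stand, and each limits what a reader might infer:

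- A reader might infer that the 55% figure is offered per site. It is not; its sentence refers to the whole sample.
- A reader might infer that allowing four unreplaced losses is itself unsound. It is not. Pooled power with 28 completers is adequate, and Section 10.6 also permits replacement up to 32. Only the stated reason fails.
- A reader might infer that site-specific drug-concentration results will be misread. Section 10.7.2 lists no per-site analysis of them, so that remains a possibility.

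The claim could also mean a contrast of effects between sites. The protocol gives no calculation for one, and the answer depends heavily on the model, so I attach no figure.

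**Conclusion.** The per-site power claim in Sections 10.4 and 10.6 is not supported by the protocol's own calculation. Power for the effect of about 65% is roughly 60-70% at a site under even losses or none, and 50-55% in the worst case that Section 10.6 allows. The sizes rest on the back-solved standard deviation, two-sided testing, the untransformed scale, and reading the requirement as 20 women. The direction needs only the last of these, since 14 to 16 is fewer than 20.

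The pooled calculation is intact, and no listed analysis of drug concentrations depends on per-site power. This is a correction that should be made, not a flaw that threatens the study.

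**What to change.** 1. Delete the per-site power wording in Section 10.4 and in the note to Section 10.6.
2. State in Section 10.4 that the 55% figure applies to the 28 completers of both sites together.
3. State that per-site power is about 60-70% for the 65% effect, with the assumptions behind it, and that per-site results are descriptive estimates with confidence intervals. If they come from a model, it needs a site-by-stage term; site as a main effect alone does not yield a coitus effect for each site.
4. Justify the rule on four unreplaced couples by pooled power (28 completers: about 92% for 65%, about 80% for 55%). Cap unreplaced losses at two per site as well as two per group, so that no site falls below 14 through unreplaced losses.

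The cost is a text change in two sections and a less favourable stated figure. No couples are added. Keeping the per-site claim instead would take 20 completers per site, 2 × 20 = 40 in all.
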